10.4.3 ANALYSIS OF THE SECONDARY ENDPOINT(S)

For the analysis of GAIS, MSS, POSAS and 5-point Likert scale secondary performance endpoints, the following analysis will be considered:

- Summary tables for differences of 1 and 2 month post treatment GAIS and MSS scores compared to baseline as evaluated by independent blinded reviewer will be displayed as mean difference, standard deviation and standard error. The point level for each of these ordinal scale assessment tools will be put into consideration where applicable.

Summary tables for differences of 3 and 10 month post treatment POSAS score compared to baseline as evaluated by independent blinded reviewer and the subjects will be displayed as mean difference, standard deviation and standard error. The point level for each of these ordinal scale assessment tools will be put into consideration where applicable.

Similarly, summary tables of 5-point Likert scale satisfaction scores assessed by the subjects at 3 and 10 month post treatment visits as well as differences between satisfaction scores at 10 months compared to 3-month post treatment visits will be displayed as mean, mean difference, standard deviation and standard error. The point level for each of these ordinal scale assessment tools will be put into consideration where applicable.

- Where applicable, bar charts, pie chart, graphs or any other descriptive statistical displays indicating scores, percentages or proportions of subjects' GAIS, MSS, POSAS and 5-point Likert scale improvement and satisfaction scores will be used to analyse performance.

- All statistical tests that will be two-sided. The level of statistical significance for effectiveness analyses is 5% ($\alpha = 0.05$) for all tests of differences. Where appropriate, Paired t-test and/or Wilcoxon Signed-Ranks Test for Matched Pairs will be used to compare the evaluation of score differences of GAIS, MSS, POSAS and 5-point Likert scale post treatment assessment. Analysis of Covariance (ANCOVA) may also be used where appropriate.

GAIS, MSS, POSAS and 5-point Likert scale scores of all subjects who received at least one treatment of Venus Viva™ system for the treatment of surgical scars following breast augmentation, abdominoplasty or face lift and for whom at least one valid post-baseline assessment were obtained will be analysed for these secondary endpoints. Multiple imputation method or modelling of available data may be used for missing data as appropriate.

10.4.4 SAFETY ANALYSES

The safety analysis will be done by analyzing spontaneous reports of adverse events (AE), subjects' completed 10 cm discomfort/pain VAS and a response questionnaire as well as analysis of immediate and short term response reports by the principal investigator from his/her observation/examination of the treated area. Appropriate Medical Dictionary for Regulatory Activities (MedDRA) code will be used to describe all spontaneously reported or other study related adverse events.

Summaries of spontaneously reported or other study related adverse events will be presented as:

- Number (%) of subjects with any AE,
- Number (%) of subjects with any serious adverse events (SAE),
- Number (%) of subjects permanently withdrawn from treatment due to AE

Summaries of analysis of immediate and short term response reports by the principal investigator examination will be displayed on a bar or pie chart as;

- the overall frequency of subjects with each event (pain during treatment, hemorrhage, burn, erythema, edema, purpura)
- Frequency of subjects with specific severity/intensity for each event using a 5 points scale: 1=none; 2=trace; 3=moderate; 4=marked; 5=severe
- The overall percentage or proportion of subject observed with marked or severe intensity of any event will be calculated and compared to those with none, trace or moderate severity/intensity with the aid of a bar or pie chart.

The following will be considered for the analysis of 10 cm discomfort/pain VAS scores safety data:

Summary table for differences of baseline post-treatment (Visit 2) and Visit 6 post-treatment 10 cm discomfort/pain VAS scores will be displayed as mean difference, standard deviation and standard error. The 10 cm discomfort/pain VAS is a 11-level (0 to 10) ordinal scale tool for assessing pain.

Bar, pie charts or graphs indicating scores, percentages or proportions of subjects with Visit 6 and baseline (Visit 2) post-treatments VAS scores difference that is < 1 and > 1 will be used to analyse subjects' tolerability of this treatment.

All statistical tests will be two-sided. The level of statistical significance for effectiveness analyses is 5% ($\alpha = 0.05$) for all tests of differences. Where appropriate, Paired t-test and/or Wilcoxon Signed-Ranks Test

for Matched Pairs will be used to compare the difference between Visit 2 and Visit 6 post treatment VAS scores.

The Paired t-test and/or Wilcoxon Signed-Ranks Test for Matched Pairs will enable us to accept or reject the null hypotheses. Rejection of null hypotheses will establish that:

- The two-sided 95% confidence interval for the difference between the means excludes zero.
- The two means are statistically significantly different at the 5% level ($P < 0.05$) two-sided.

Upon rejection of null hypotheses, further statistical test tools such as Confidence Interval and/or t-test will be used to test expected safety endpoint; that is alternative hypothesis, $H_a \leq 1$.

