4.2.2 SECONDARY PERFORMANCE ENDPOINTS

- Improvement in appearance of surgical scars at 1 and 2 months post-treatment as evaluated by independent blinded reviewer using the General Aesthetic Improvement Scale (GAIS) and Manchester Scar Scale (MSS).
- Assessment of surgical scars at 3 and 10 months post-treatment as evaluated by independent blinded reviewer using the Patient and Observer Scar Assessment Scale (POSAS).
- Assessment of surgical scars at 3 and 10 months post-treatment as evaluated by the subject using the Patient and Observer Scar Assessment Scale (POSAS).
- Subjects' assessment of satisfaction (5-point Likert Scale) with the treatment at 3 and 10 months post-treatment.

Safety endpoints:

- Subject's assessment of discomfort and pain after treatment as measured by a 10 cm visual analog scale (VAS).
- Subjects experiencing a treatment-related adverse event (AE) by 10 months post-treatment.

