8.4 REPORTING PROCEDURES

8.4.1 ADVERSE EVENT REPORTING

All AEs will be recorded on the appropriate CRF and will include information about the start and stop dates, severity and relatedness. There should be an attempt to report a "diagnosis" rather than the individual signs, symptoms and abnormal laboratory values associated with the diagnosis. However, a diagnosis should be reported only if, in the Investigator's judgment, it is relatively certain (i.e., definite or possible). Otherwise individual signs, symptoms and abnormal laboratory values should be reported as distinct adverse events.

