10.3 ANALYSIS DATASETS

Modified Intention-to-Treat Analysis Dataset will be used; performance and safety analyses will be carried out on all subjects who received at least one treatment of Venus Viva™ system and for whom at least one valid post-baseline performance and safety evaluation were obtained.

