10.4.2 ANALYSIS OF THE PRIMARY PERFORMANCE ENDPOINT(S)

The following will be considered for the analysis primary performance endpoint:

Summary table for differences of baseline, 3-month and 10-month post treatment General Aesthetic Improvement Scale (GAIS) and Manchester Scar Scale (MSS) scores will be displayed as mean difference, standard deviation and standard error. The General Aesthetic Improvement Scale (GAIS) scores is a 5-point scale improvement assessment chart while Manchester Scar Scale (MSS) is two scales whose scores are combined - an overall VAS and seven scar parameters.

Bar, pie charts or graphs indicating scores will also be used to analyse performance, where applicable.

All statistical tests will be two-sided. The level of statistical significance for effectiveness analyses is 5% ($\alpha = 0.05$) for all tests of differences. Where appropriate, Paired t-test and/or Wilcoxon Signed-Ranks Test for Matched Pairs will be used to compare the evaluations of General Aesthetic Improvement Scale (GAIS) scores and Manchester Scar Scale (MSS) scores at 3 and 10 months against baseline. Analysis of Covariance (ANCOVA) may also be used where appropriate.

The Paired t-test and/or Wilcoxon Signed-Ranks Test for Matched Pairs will enable us to accept or reject the null hypotheses. Rejection of null hypotheses will establish that:

- The two-sided 95% confidence interval for the difference between the means excludes zero.
- The two means are statistically significantly different at the 5% level ($P < 0.05$) two-sided.

Upon rejection of null hypotheses, further statistical test tools such as Confidence Interval and/or t-test will be used to test expected primary performance endpoint; that is alternative hypothesis that $H_a \geq 1$. This will be used to determine if the study meets the primary performance endpoint.

General Aesthetic Improvement Scale (GAIS) scores and Manchester Scar Scale (MSS) scores of all subjects who received at least one treatment of Venus Viva™ system for the treatment of surgical scars following breast augmentation, abdominoplasty or face lift and for whom at least one valid post-baseline GAIS and MSS assessment were obtained will be analysed for the primary endpoint. Multiple imputation method or modelling of available data may be used for missing data as appropriate.

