10.4.5 ADHERENCE AND RETENTION ANALYSES

Adherence to the protocol will be assessed by calculating the number (%) subjects' data for each endpoint assessment that is not provided in subjects Case Report Forms. This will be further analyzed as per frequency of each endpoint data that is not available due to loss to follow-up, discontinuation of the intervention or any other reason.

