10.5 SAMPLE SIZE

One of the primary performance endpoints outcome measures was used to calculate the study sample size.

Sample size calculation using the subject's improvement of surgical scars at 3 months post-treatment as evaluated by independent blinded reviewer using the General Aesthetic Improvement Scale (GAIS);

- Null and alternate hypotheses:
 - **Null Hypothesis ($H_0: \mu_d = \mu_{post} - \mu_{pre} = 0$)** – There is no improvement of surgical scars at 3 months post-treatment review compared to baseline.
 - **Alternative Hypothesis ($H_a: \mu_d = \mu_{post} - \mu_{pre} \neq 0$)** – There is improvement of surgical scars at 3 months post-treatment review compared to baseline. The improvement of surgical scars will be defined by General Aesthetic Improvement Scale (GAIS) scores evaluated by independent blinded reviewer. Expected mean improvement difference is not less than one (1) GAIS score higher than baseline.
- In view of the nature of this study in regard to treatment period of 3 months and up to 10 months follow-up, we make provision for 30% study drop out, withdrawal or loss to follow-up.
- Due to the natures of 3 types of surgical scars that will be treated in this clinical study, the study will be viewed as 3 groups of cohort studies;
 - breast augmentation cohort group
 - abdominoplasty cohort group
 - face lift cohort groupThe study's sample size calculation below is number of subjects required for each group the makes up the study
- 2-Tailed Sample Size calculation formula for Matched Samples was used in the table below:

(1- β), Power	0.9
α , Level of Significance	0.05
μ_d , mean difference; this is the expected improvement (difference) to treatment assessed by GAIS scores under H_a	1.0
σ_d , Standard Deviation of the difference scores (GAIS range $\div 4$) = [4 \div 4]	1.0
ES, Effect Size $[(\mu_d/\sigma_d)]$	1.0
$Z_{1-\alpha/2}$	1.96
$Z_{1-\beta}$, (for 90%)	0.84
Estimated Sample Size	10.51 \approx 11
Estimated Sample Size + 30% drop out	14.30 \approx 15

Conclusion: The estimated sample size for each cohort group obtained from the primary performance endpoint outcome measure calculation plus 30% drop out provision that will be used for this study is 15.

The study will enroll up to 50 female subjects requesting treatment of surgical scars following breast augmentation or abdominoplasty and up to 25 male and female subjects requesting treatment of surgical scars following face lift surgery.

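### The AE summaries in 10.4.4 do not estimate the stated 10-month safety endpoint: no treatment-related count, no handling of follow-up that ends before Month 12, and two different safety denominators

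*Combined protocol and SAP*

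**What the plan says.** Section 4.2.2 and the Protocol Summary give the AE endpoint as "Subjects experiencing a treatment-related adverse event (AE) by 10 months post-treatment". The third treatment is at Month 2 (7.3.3), so 10 months later is the final visit at Month 12 (7.3.4).

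Section 10.4.4 plans three AE summaries: "Number (%) of subjects with any AE", the same for SAEs, and the same for permanent stopping of treatment because of an AE. None is restricted to treatment-related events, none refers to length of follow-up, and the denominator is not stated there.

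On who is analysed, 10.3 says "performance and safety analyses will be carried out on all subjects who received at least one treatment of Venus Viva™ system" and adds the condition "for whom at least one valid post-baseline performance and safety evaluation were obtained". The Protocol Summary says that everyone treated at least once is analysed, without that condition. Neither requires completed follow-up.

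On incomplete data:
- Section 10.5: "we make provision for 30% study drop out, withdrawal or loss to follow-up".
- Section 10.4.2: "Multiple imputation method or modelling of available data may be used for missing data as appropriate". Section 10.4.3 repeats this for the secondary performance endpoints; 10.4.4 has no counterpart.
- Section 10.4.5 tabulates the "frequency of each endpoint data that is not available due to loss to follow-up, discontinuation of the intervention or any other reason".

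The data for a time-based estimate are already collected. Section 8.4.1 says "All AEs will be recorded on the appropriate CRF and will include information about the start and stop dates, severity and relatedness", and 8.3 has the investigator ask about AEs at every visit.

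**The concern.** Whether a subject is free of a treatment-related AE at 10 months is known only if that subject was followed to Month 12. The plan foresees withdrawal, loss to follow-up and termination (5.5.1, 8.4.4), and no visit is scheduled between Month 5 and Month 12. A crude percentage treats a subject last seen at Month 5 with no event as a known non-event at Month 12. Shortened follow-up can miss events but cannot create them. For subjects in the analysis set, the crude figure can therefore only equal or fall below their full-follow-up risk, and any error favours the device. Pigment change and scarring are among the expected harms (8.2.3), and some of these may appear late.

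Two further gaps concern the same table. The stated endpoint is limited to treatment-related events, but no listed summary is. And the two definitions of the analysed population can give different denominators.

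**Working it through.** **The plan's own figure.** No AE rate or AE precision is stated. The only related figure is the 30% provision in 10.5: 11 × 1.30 = 14.3, rounded up to 15 per cohort. This reproduces. It is an allowance for the sample size, not a forecast of loss in the safety set.

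**Set-up.** Let p be the true risk by Month 12, d = 0.30 the proportion lost, C the time of loss and F(t) the risk by month t. If loss is unrelated to AE risk and every treated subject is in the denominator:

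crude % = (1 − d) × p + d × mean of F(C).

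The second term cannot be negative, so crude/true is at least 1 − d = 0.70. This is the 30% bound.

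**Assumptions.** p = 20% is illustrative. Event timing is (a) within 3 days of the treatments at Months 0, 1 and 2; (b) a constant rate over 12 months; or (c) evenly spread over Months 5 to 12. Loss is either uniform over 12 months or all at Month 5.

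**(a) Around treatment.** The mean event time is 1 + 0.5 × 3/30.4 = 1.05 months. Under uniform loss, a lost subject's event is seen with probability 1 − 1.05/12 = 0.913. Crude = 0.20 × (0.70 + 0.30 × 0.913) = 19.5%. With loss at Month 5 all events are seen: 20.0%.

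**(b) Constant rate.** F(t) = 1 − 0.8^(t/12).
- Uniform loss: mean F(C) = 1 − 0.20/0.2231 = 0.1037, where 0.2231 = −ln 0.8. Crude = 0.140 + 0.30 × 0.1037 = 17.1%; shortfall 2.9/20 = 14.4%.
- Loss at Month 5: F(5) = 1 − 0.8^(5/12) = 0.0888. Crude = 0.140 + 0.30 × 0.0888 = 16.7%; shortfall 3.3/20 = 16.7%.

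**(c) Months 5 to 12 only.**
- Uniform loss: a lost subject's event is seen with probability 7/12 × 1/2 = 0.292. Crude = 0.20 × (0.70 + 0.30 × 0.292) = 15.8%.
- Loss at Month 5: 0.20 × 0.70 = 14.0%.

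**Effect of the 10.3 condition.** The first scheduled post-baseline photographs, GAIS and MSS are at Month 3 (7.3.3, 7.3.7). Read literally, 10.3 drops subjects lost before then unless an exit visit supplies an assessment. Under uniform loss that is 0.30 × 3/12 = 7.5% of subjects, so the denominator is 0.925. For (b), the mean of F over Months 3 to 12 is 0.129, and crude = (0.140 + 0.225 × 0.129)/0.925 = 18.3%. For (c), crude = 0.1575/0.925 = 17.0%. With loss at Month 5 nobody is dropped, so nothing changes.

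| Event timing (true risk 20%) | Uniform loss, all treated | Uniform loss, 10.3 read literally | Loss at Month 5, either denominator |
|---|---|---|---|
| (a) Around treatments | 19.5% | 20.0% | 20.0% |
| (b) Constant rate | 17.1% | 18.3% | 16.7% |
| (c) Months 5 to 12 only | 15.8% | 17.0% | 14.0% |

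Simulation with 1,000,000 subjects per setting agrees to within about 0.1 point, and Kaplan-Meier returned 19.9% to 20.1% in the all-treated settings above. At true risks of 10% to 40%, the constant-rate crude/true ratio stays at 0.83 to 0.86. With 75 subjects at 20% risk, 15.0 events would be expected with full follow-up. The crude count would be 12.5 under (b) with loss at Month 5, and 10.5 at the bound.

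**The case against.** The strongest case against has five parts.

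1. Most expected effects in 8.2.3 are acute (pain, redness, swelling, crusting, blistering, burns), and 7.3.3 schedules an examination 2 to 3 days after each treatment. If AEs follow that pattern, the crude figure is nearly right. This stands, and it is why the point says the risk can be understated, not that it is.
2. A reader might infer that every subject lost without an event is scored as event-free. The documents do not support that. Under a literal 10.3, those lost before a post-baseline performance assessment leave the set, and any AEs they had leave with them. That bias can go either way. Subjects terminated for an AE are already in the numerator.
3. The listed line counts any AE. Unrelated events raise it, so its net direction against the treatment-related endpoint is unknown. This is correct, but it confirms that the endpoint itself is not tabulated. The lead-in in 10.4.4 mentions study-related events but pools them with spontaneous reports, so it does not supply the count.
4. Mitigations exist: best-effort exit visits (5.5.2, 7.3.5), retention contact (5.4) and the missing-data table in 10.4.5. They may reduce loss or make it visible, but they do not change the percentage.
5. No hypothesis or success rule uses the AE percentage; the only safety hypothesis concerns the VAS (10.2). At 20% risk and 75 subjects the standard error is √(0.2 × 0.8/75) = 4.6 points, larger than the 3.3-point shortfall under a constant rate with loss at Month 5. Both facts limit the consequence. Still, a one-directional error that can be removed from data already on the CRF is worth removing.

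**Conclusion.** The point holds in a limited form. Section 10.4.4 contains no estimate of the stated safety endpoint: no treatment-related line, no treatment of follow-up ending before Month 12, and no settled denominator. For subjects lost event-free after entering the analysis set, the 10-month risk can be understated. The shortfall is close to nil if AEs cluster around treatment, about 14% to 17% relative under a constant event rate with all treated subjects counted, and at most 30% relative if all events follow the loss.

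These sizes assume 30% loss unrelated to AE risk; event rates and timing are assumptions because the documents give none. A reader might go further and infer that the reported AE percentage will certainly be too low. The documents do not support that: timing may make the shortfall negligible, and the any-AE line includes unrelated events that push the other way. If loss is related to AEs, the 30% bound no longer applies and Kaplan-Meier does not remove the bias.

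**What to change.** In 10.4.4:
- Define the safety denominator as all subjects treated at least once, and align 10.3 with the Protocol Summary.
- Keep the crude counts and add a number (%) line for treatment-related AEs, stating which relationship categories in 8.2.2 count as related.
- Add the Kaplan-Meier risk of a first treatment-related AE at 10 months post-treatment (Month 12) with a 95% CI. Measure time from first treatment, use the recorded AE start dates, and censor event-free subjects at their last AE enquiry.
- Show the number still followed at Months 3, 5 and 12, counting attendance within the visit window.
- State that Kaplan-Meier assumes non-informative loss.

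Separate curves for pigment change and scarring are optional, since they would be imprecise in at most 75 subjects.

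The cost is SAP wording and one extra table from data already collected; 10.1 allows a revised plan to be issued before database lock. The downside is that the reported risk may be slightly higher than the crude percentage.

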The investigator will examine the treated areas and report immediate and short term response (30 minutes post-treatment) (pain during treatment, hemorrhage, burn, erythema, edema, purpura) using a 5-point scale: 1=none; 2=trace; 3=moderate; 4=marked; 5=severe.

The assessment of discomfort/pain based on the subject's completion of the 10 cm VAS should also be documented immediately after each treatment.

The normal response to these treatments is transient erythema and edema. If any other side effects occur, as indicated in the protocol, they must be recorded.

Subjects will be discharged from the clinic and will be instructed to return in 2-3 days in order to be examined for adverse events.

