 - **Null Hypothesis ($H_0: \mu_d = \mu_{post} - \mu_{pre} = 0$)** – There is no improvement of surgical scars at 3 and 10 months post-treatment review compared to baseline.
Alternative Hypothesis ($H_a: \mu_d = \mu_{post} - \mu_{pre} \neq 0$) – There is improvement of surgical scars at 3 and 10 months post-treatment review compared to baseline. The improvement of surgical scars will be defined using Patient and Observer Scar Assessment Scale (POSAS) scores evaluated by the subject.
 - **Null Hypothesis ($H_0: \mu_d = \mu_{post} - \mu_{pre} = 0$)** – There is no satisfaction with treatment as documented on a 5-point Likert scale at 3 and 10 months compared to baseline.
Alternative Hypothesis ($H_a: \mu_d = \mu_{post} - \mu_{pre} \neq 0$) – There is satisfaction with treatment as documented on a 5-point Likert scale at 3 and 10 months compared to baseline. The satisfaction with treatment will be defined by 5-point Likert scale at 3 and 10 months compared to baseline as assessed by the subjects.
- Safety Endpoint:
 - **Null Hypothesis ($H_0: \mu_d = \mu_{post} - \mu_{pre} = 0$)** – There is no difference in subjects' 10 cm discomfort/pain VAS score experienced after at Visit 6 treatment and that of baseline treatment (Visit 2).
Alternative Hypothesis ($H_a: \mu_d = \mu_{post} - \mu_{pre} \neq 0$) – There is a difference in subjects' 10 cm discomfort/pain VAS score experienced after at Visit 6 treatment and that of baseline treatment (Visit 2). Expected mean difference is maximum VAS score ≤ 1 .

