10.4.6 BASELINE DESCRIPTIVE STATISTICS

Subjects baseline scores of all endpoints (GAIS, MSS and POSAS) will be compared using descriptive statistics such as mean score, standard deviation, standard error, range and graphical presentations.

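### Subject-reported pain is analysed only as a change from Visit 2 to Visit 6, and its limit of 1 is tested only after zero change is rejected

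*Combined protocol and SAP*

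**What the plan says.** Section 4.2.2 and the protocol summary list two safety endpoints. One is the subject's "assessment of discomfort and pain after treatment as measured by a 10 cm visual analog scale (VAS"). Section 7.3.2 says that "completion of the 10 cm VAS should also be documented immediately after each treatment", and section 7.3.3 repeats the VAS at the second and third treatments, so scores exist for Visits 2, 4 and 6.

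The planned analyses of those scores are:

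- **Hypothesis (10.2):** the null is no difference between the Visit 6 and Visit 2 scores. The section adds "Expected mean difference is maximum VAS score" of at most 1.
- **Table (10.4.4):** "Summary table for differences of baseline post-treatment (Visit 2) and Visit 6 post-treatment 10 cm discomfort/pain VAS scores will be displayed", as mean difference, SD and SE.
- **Chart (10.4.4):** "proportions of subjects with Visit 6 and baseline (Visit 2) post-treatments VAS scores difference that is" below 1 and above 1, offered as the tolerability analysis.
- **Test (10.4.4):** paired t-test and/or Wilcoxon signed-rank, Visit 2 against Visit 6, two-sided 5%.
- **Limit (10.4.4):** "Upon rejection of null hypotheses, further statistical test tools such as Confidence Interval and/or t-test will be used to test expected safety endpoint", meaning the alternative that the difference is at most 1.

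**The concern.** The endpoint is a level of pain, but everything planned for it is a change between two post-treatment scores. A subject scoring 1 at both visits and a subject scoring 8 at both visits contribute the same difference, 0. The table, chart and test cannot tell them apart, and the Visit 4 score is used nowhere. The report could state that pain did not change without any summary of how much pain subjects reported.

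The order of testing is a separate problem. Rejecting zero first is at least compatible with showing a benefit, and section 10.4.2 uses that order for the primary endpoint. For an upper limit on harm, no change is a favourable result, yet it is the result that usually stops the limit from being tested.

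Two smaller points follow from the same text. A subject who stops before Visit 6 has no paired difference and leaves the VAS analysis. A difference of exactly 1 falls in neither chart group, although the stated limit includes it.

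**Working it through.** **Is the level summarised anywhere else?** The other candidate sections are:

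- 10.4.1 sets what a summary table contains, not which tables are produced. The only VAS table named is of differences.
- 10.4.3 specifies the mean as well as the mean difference for the satisfaction score. 10.4.4 does not do so for the VAS.
- 10.4.6 says "Subjects baseline scores of all endpoints (GAIS, MSS and POSAS) will be compared using descriptive statistics"; the VAS is not in that list.
- 10.4.10 gives listings of individual data, which are not a summary.
- 10.4.4 also plans frequencies of pain during treatment on a 5-point scale. That is the investigator's rating, not the subject's.

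**What does the testing order cost?** The documents give no power or SD for the VAS, so there is no stated figure to reproduce.

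Inputs:

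- Two-sided alpha 0.05 and limit 1, from 10.4.4.
- n = 75 × 0.70 = 52.5, taken as 52, from the enrolment ceiling and drop-out allowance in 10.5. Because 75 is an upper figure and the 30% covers drop-out to 10 months, n = 75 is shown too. So is n = 11, the evaluable size per cohort in 10.5.
- SD of the Visit 6 minus Visit 2 difference: **assumed** 1, 2 or 3.
- Normal differences, paired t-test.

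Let d be the mean difference, s its sample SD, and h = t(0.975, n−1) × s/√n.

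- As planned: success needs |d| > h **and** d + h ≤ 1.
- Direct: success needs only d + h ≤ 1.

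If the true change is 0, |d| > h has probability 0.05 whatever n or SD. Half of those rejections (2.5%) are falls in pain and always meet the limit. The other half are rises, which meet it only if the whole interval fits between 0 and 1, so h must be below 0.5. At n = 52 and SD 2, h is about 2.008 × 2/√52 = 0.557, so few do. Planned success must therefore lie between 2.5% and 5%.

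Probability of showing the limit when the true change is 0:

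| n | Rule | SD 1 | SD 2 | SD 3 |
|---|---|---|---|---|
| 52 | planned | 5.0% | 2.8% | 2.5% |
| 52 | direct | >99% | 94% | 65% |
| 75 | planned | 5.0% | 4.1% | 2.5% |
| 75 | direct | >99% | 99% | 81% |
| 11 | planned | 3.2% | 2.5% | 2.5% |
| 11 | direct | 85% | 32% | 17% |

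Hand check, n = 52, SD 2, direct: SE = 2/√52 = 0.277; Φ(1/0.277 − 2.008) = Φ(1.60) = about 0.945, close to the 94% in the table.

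Other true changes, n = 52, SD 2:

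| True change | Planned | Direct |
|---|---|---|
| −1 | 94% | >99% |
| −0.5 | 42% | >99% |
| +0.5 (within the limit) | 1.3% | 42% |

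**How many subjects could sit at exactly 1?** Section 10.4.4 treats the scale as 11 levels, 0 to 10. If differences are normal with mean 0 and rounded to whole points, the share is Φ(1.5/SD) − Φ(0.5/SD) = 0.242, 0.175 and 0.125 at SD 1, 2 and 3.

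**Who is in the analysis?** Section 10.3 requires a treated subject "for whom at least one valid post-baseline performance and safety evaluation were obtained". In the schedule of events the first reviewer scores after baseline are at Visit 8, so someone who stops early can have a VAS score and still fall outside the dataset.

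**The case against.** The case against has four parts.

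- **The level is unspecified rather than excluded.** Section 10.4.4 says safety will be analysed from the completed VAS and introduces its list as things to be considered. Every score will appear in a listing, and 10.1 allows a revised SAP before database lock. This softens the wording but leaves no commitment to a summary, and the contrast with the satisfaction score in 10.4.3 is hard to explain away.
- **A reader will have some absolute information.** Investigator-rated pain by severity, adverse event counts, withdrawals due to adverse events, and missing data by reason are all planned. That is true, but none of them summarises what subjects reported.
- **The value 1 carries little weight.** Section 10.2 calls it expected, its wording is unclear, and 10.4.4 lacks the sentence in 10.4.2 that makes the corresponding check decide the primary endpoint. The mean difference, SD and SE are shown either way, so a reader can form the confidence bound. It is right that the order blocks the formal conclusion and not the data. But 10.4.4 itself presents the check as a test of the expected safety endpoint, so its order matters.
- **The sizes rest on assumed SDs, and the 5% is exact only for a t-test on normal data.** With a Wilcoxon test on whole-point scores it would differ somewhat, and in a cohort of 11 even the direct check is weak at SD 2 or 3. The direction is the same at every n and SD examined.

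The chart cut-point is minor: it affects a descriptive display, and exact ties at 1 would be uncommon if the line were measured continuously.

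**Conclusion.** The concern holds. The plan specifies no mean, median or distribution of subject-reported pain after any treatment, although that is one of its two named safety endpoints. This part needs no numerical assumption.

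The order of testing withholds the favourable conclusion when pain is stable. Under zero change the limit is tested in 5% of trials. At n = 52 it would be shown in 2.5% to 5.0% of trials across assumed SDs of 1 to 3, against 65% to more than 99% if tested directly. The loss is small when pain clearly falls and greatest when pain is unchanged or rises slightly.

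The primary endpoint and data collection are unaffected. The point should be corrected before database lock.

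**What to change.** Amend sections 10.2 and 10.4.4:

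1. Add a table of the VAS score after each treatment (Visits 2, 4 and 6) with mean, median, 95% CI and distribution, in all subjects treated at least once, including those who stop early. State this population explicitly, because the 10.3 dataset also requires a performance evaluation after baseline.
2. Keep the Visit 6 minus Visit 2 analysis, since section 7.3.1 lets treatment settings vary between visits. State clearly that 1 is an upper limit on the mean change, and check whether the upper bound of the two-sided 95% CI is at or below 1, without first rejecting zero.
3. Chart subjects as at most 1 against above 1.

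The cost is SAP wording and one further table. The VAS is already collected after every treatment.
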